VIEWS ON COVID-19 AND VACCINATION STUDY PROTOCOL

VIEWS ON COVID-19 AND VACCINATION

NCT04706403

Principal Investigator:

[name], MA

Associate Professor, Department of Medicine, UMass Chan Medical School

Supported by:

This project has been funded in whole or in part with federal funds from the National Library of Medicine, National Institutes of Health, under Cooperative Agreement *UG4LM012347* with the University of Massachusetts, Worcester.

Last Updated and Approved: January 15, 2021

1. Title

If We Build It, Will They Come? A Pilot Study to Develop and Test Messages to Maximize Uptake of Coronavirus Vaccine When Available.

2. External IRB Review History*

N/A

3. Prior Approvals:

N/A

4. Objectives*

This study aims to develop evidence-based messages that effectively mitigate concerns of people at risk for not being vaccinated against COVID-19, with the ultimate goal of maximizing vaccine uptake in vulnerable populations when a COVID-19 vaccine becomes available. To achieve our goals, we will accomplish two objectives:

- (1) Gain an in-depth, current understanding of factors influencing vaccine hesitancy in vulnerable populations.
- (2) Develop and test messages that effectively address concerns of vaccine-hesitant subgroups at risk for declining to be vaccinated, providing an evidence base to inform future outreach efforts.

5. Background*

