Our team recently surveyed a nationally representative sample of approximately 1,000 adults in the United States and found that only 57% intended to be vaccinated when a coronavirus vaccine becomes available.¹ This percentage was even lower among people who identified as Black or Hispanic (39% and 43% respectively), those with a high school education or less (46%) and those in the lowest income groups (49% of those reporting a household income of \$30,000 or less, compared to 72% of those reporting a household income of \$100,000 or more). We asked those who indicated they would not or might not get vaccinated for their reasons and found that some individuals may be willing to be vaccinated if provided specific information about the vaccine such as side effects and effectiveness. Others expressed generalized skepticism, fear and distrust of vaccines, with some even referring to anti-vaccine conspiracy theories. Our findings are consistent with an extensive body of research documenting that people often do not behave rationally and highlight the urgent need to proactively develop and test interventions to maximize vaccination rates when a coronavirus vaccine becomes available.²⁻⁶ To address this need, our goals in the present study are to create and test targeted messages to address the concerns of subgroups of people at risk for not being vaccinated, with the ultimate goal of maximizing vaccine uptake when a vaccine for COVID-19 becomes available. We will accomplish this by working with an existing online panel of volunteers, which will allow efficient, focused data gathering. Results of the first round of the survey will provide a nuanced, current description of how vulnerable adults perceive the coronavirus and forthcoming vaccines, which will be used as the basis for developing messages and communication strategies. In the second round, we will test different versions of messages intended to reduce vaccine hesitancy and support uptake. This project will ultimately result in a set of tested, evidence-derived messages about vaccination for COVID-19. We will make these messages available, together with evidence how these influence members of vulnerable populations' understanding of vaccination, and disease risk, as well as intent to be vaccinated. The messages will be freely available for use by organizations and providers seeking to improve communication about a coronavirus vaccine.

6. Inclusion and Exclusion Criteria*

Inclusion Criteria.

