Participants will be recruited from an existing online research panel (Prolific). Prolific verifies participants at the time they register with Prolific and assigns participants a Prolific study ID. Prolific will post the invitation to our survey to the dashboard of eligible participants registered on their site. The survey title, duration, and payment amount will be displayed in the dashboard of eligible participants, as well as a link to the online survey. Surveys will be programmed in Research Electronic Data Capture (REDCap) - an online survey application. Participants' survey responses will be collected anonymously.

If a participant elects to respond to the survey, they will be taken to a REDCap survey. The survey will include questions that assess participants' intent to be vaccinated when a COVID-19 vaccine is available, as well as participants' knowledge, beliefs, and attitudes about COVID-19, vaccines in general, and a COVID-19 vaccine.

In one section of the survey, we will ask participants to imagine they are at a routine follow up visit with their primary care provider. Participants will be randomized to several brief, hypothetical messages from their provider regarding vaccination after which participants' intent to be vaccinated will be re-assessed. See table 1 for questionnaire domains and sample items.

Table 1. Sample Survey Domains and Items

Sample Domains	Sample Items
Personal risk I – disease overall	What is your best guess as to whether you will get the coronavirus within the next 6 months ?
Vaccination intent	When a vaccine for the coronavirus becomes available, will you get vaccinated?
Message testing	Imagine that you are seeing your doctor for an annual physical exam. Near the end of the appointment, your doctor says, “We have the COVID-19 vaccine available today. I’ve taken a careful look at the studies and the results are very impressive. They show that it’s very safe and very effective. This is the best way to protect yourself from this virus. I recommend you get it.”
Risk Beliefs	The COVID-19 pandemic is a hoax.
Knowledge of COVID-19	If 100 people your age were infected with COVID-19, about how many would need to be hospitalized?

Attitudes towards vaccine - general	Vaccines are one of the most important medical advances ever developed.
Attitudes towards COVID-19 vaccine specifically	The COVID-19 vaccine has been developed too quickly.
Vaccine knowledge	Vaccines don't work against viruses.

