Vaccination norms and values	Most of the people I know will get vaccinated against COVID-19.
Personal experience with COVID-19	Have any of your friends and family members have become very ill or died of COVID-19?
Vaccination behavior (past and future)	Thinking back over the past 5 years, how many of those years did you get a flu shot?
Demographics and other characteristics	Age, gender, education, etc.

Participants will receive a small payment as recommended by the panel vendor, valued at approximately \$3.00 to \$3.50 for a 20-minute survey. The final amount will depend on the final estimated survey completion time and an hourly rate selected to maximize participation and the number of participants. The hourly rate range required by the survey vendor is \$6.50/hr- \$12.50/hr). Payment will be made directly by the online research panel to participants after survey completion.

12. Data and Specimen Banking*

No specimens are being collected as part of the research. We will maintain a limited dataset for analysis at the completion of the study.

13. Data Analysis and Management*

Data will be stored on University of Massachusetts Medical School computers and/or Meyers Primary Care Institute computers. We will not collect any information that will allow us to identify participants. All contact with participants will be via the online vendor, which has assigned a unique study id to each participant.

We will examine response distributions of each variable and associations between variables (e.g., correlations between perceived personal risk and tendency to engage in protective behavior).

We will test the impact of different communication strategies that providers might use to recommend COVID-19 vaccination using t-tests, chi-squares, and regression models to compare vaccination intent according to which message participants received. Appropriate statistical tests will be chosen depending on specific variables and their distributions.

14. Provisions to Monitor the Data to Ensure the Safety of Subjects*

The proposed study involves no more than minimal risk to participants.

To ensure that participants have access to current, accurate information about the coronavirus, we will provide the web address to the main Centers for Disease Control (CDC) website (<https://www.cdc.gov/>), which contains information and resources related to the coronavirus pandemic.

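### No reference arm without a recommendation is described, so the randomised comparison can rank the messages but cannot show whether any of them raises or lowers vaccination intent

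*Combined protocol and SAP*

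**What the plan says.** Objective 2 (Section 4) is to "Develop and test messages that effectively address concerns of vaccine-hesitant subgroups at risk for declining to be vaccinated". Section 5 adds: "In the second round, we will test different versions of messages intended to reduce vaccine hesitancy and support uptake". It also undertakes to release the messages "together with evidence how these influence members of vulnerable populations' understanding of vaccination, and disease risk, as well as intent to be vaccinated".

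On design, Section 11 says "Participants will be randomized to several brief, hypothetical messages from their provider regarding vaccination", after which "intent to be vaccinated will be re-assessed". The number of messages, their wording and the allocation ratio are not given. Table 1 offers samples only. The one sample message sets the scene with "We have the COVID-19 vaccine available today" and closes with the doctor's recommendation. The sample intent item is "When a vaccine for the coronavirus becomes available, will you get vaccinated".

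On analysis, Section 13 presents the messages as ways in which a provider could recommend the vaccine, and plans to test them "using t-tests, chi-squares, and regression models to compare vaccination intent according to which message participants received". No message is named as reference and no analysis of before/after change is stated. Section 10 makes intent the primary endpoint without saying whether it is the post-message value or the change. Section 25 gives an N of 1000 to 3500, with no sample-size calculation and no split between the two rounds.

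**The concern.** A comparison among recommendations answers which recommendation does better. Objective 2 and Section 5 also ask whether the messages work, that is, whether intent is higher after hearing them than it would have been without them. If every arm contains a recommendation, any effect they share cancels from every contrast. A null result would then fit messages that all help, that all do nothing, or that all backfire, and even a clear winner might be no better than the same visit with no recommendation. The messages are meant for free use by organisations and providers, so users would want to know which of these is true. A randomised reference cannot be added once the data are in.

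**Working it through.** The plan states no alpha, power, effect size or number of arms, so there is no planned figure to reproduce. The core point needs no assumed numbers; the sizes below do.

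**1. What the between-message contrast identifies.** Write intent after message j as p_j = p_0 + d + e_j, where p_0 is intent after the same visit with no recommendation, d is the effect shared by all messages, and e_j is what is particular to message j. Then p_j − p_k = e_j − e_k. Both p_0 and d drop out, so the contrast ranks messages and carries no information on d.

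Numerical check: four equal arms, chi-square on 3 df, 40,000 simulated trials per setting, common intent 57%, 62% or 67% (d = 0, +5 or +10 points). Rejection was 4.8% to 5.1% throughout.

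**2. Whether before/after change fills the gap.** Change in arm j is d + e_j + v + r + a, where v is the effect of imagining the visit, r that of being asked again, and a that of any move from a future vaccine to one available now. Only the sum is observed. The term a is inferred from the two sample items in Table 1; the re-ask wording is not given, so it is possible rather than documented. In a reference arm with the same visit, availability statement and re-ask, change is v + r + a, and subtraction leaves d + e_j.

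**3. Precision with and without the arm.** Assumed: four messages, one per person, yes/no intent, equal arms, no exclusions, all N in the message round. Intent is set at 57%, which is the team's earlier national survey (Section 5), not this panel.

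Unadjusted 95% half-width = 1.96 × sqrt(2 × 0.57 × 0.43 / n). Adjusted for pre-message intent at an assumed correlation of 0.5, multiply by sqrt(1 − 0.25) = 0.866. For Dunnett over four contrasts, replace 1.96 by 2.441.

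| N | Arms | n per arm | Unadjusted | Adjusted | Adjusted, Dunnett |
|---|---|---|---|---|---|
| 1000 | 4, no reference | 250 | 8.7 | 7.5 | – |
| 1000 | 5, with reference | 200 | 9.7 | 8.4 | 10.5 |
| 3500 | 4, no reference | 875 | 4.6 | 4.0 | – |
| 3500 | 5, with reference | 700 | 5.2 | 4.5 | 5.6 |

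Like for like, the extra arm widens intervals by sqrt(250/200) = 1.118, about 12%, adjusted or not. The adjusted formula is slightly optimistic for a yes/no item: simulation at correlation 0.5 gave 8.6 to 8.7 rather than 8.4 at N=1000.

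**4. Power of message versus reference.** Unadjusted Wald tests with Holm over four contrasts, reference intent 57%, every message with the same true effect. Chance that at least one message is significant:

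| Effect | N=1000 | N=3500 | N=1000, half in message round | N=3500, half in message round |
|---|---|---|---|---|
| +5 points | 20% | 56% | 12% | 31% |
| +10 points | 64% | 99% | 38% | 87% |

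**5. Hesitant participants.** If 43% (100% − 57%) are hesitant at the first ask, n per arm is 0.43 × 200 = 86 or 0.43 × 700 = 301. With 10% to 30% intent in the reference arm, the unadjusted half-width 1.96 × sqrt(2q(1 − q)/n) is 9.0 to 13.7 points (N=1000) or 4.8 to 7.3 (N=3500).

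**The case against.** **The arms are not listed.** Table 1 contains samples, the messages are to be developed from the first round, and a neutral message could be among the several. This stands as a limit on the claim. A reader might infer that the trial has no control; the documents show only that none is described. Section 13's description of the messages as ways to recommend vaccination leans towards there being none but does not settle it. The reference condition does not depend on the final message wording, so it can be stated now.

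**Ranking is a legitimate aim for a pilot.** Agreed: head-to-head comparison is valid for relative effects, and a plan that claimed only those would need no reference arm. Objective 2 and Section 5 claim more, so either the design or the claim should move.

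**Intent is measured before and after.** The change could suggest a rise, but it is not a randomised contrast and is not a stated analysis. Nor should one infer that Section 13 rules out using pre-message intent. It plans regression without listing covariates; it is silent.

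**Baseline adjustment might seem to pay for the extra arm.** It does not, because adjustment is equally available without that arm. The cost is about 12% in interval width either way.

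**The sizes rest on assumptions.** They do, and they describe the remedy rather than the defect. A reader might also infer an inflated familywise error from the absence of a multiplicity rule. The plan does not say that all pairs will be tested at an unadjusted level, so no such figure is claimed.

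**Conclusion.** The point holds for the design as described: randomisation supports relative effects between messages, but not whether any message raises or lowers intent. Objective 2 and the Section 5 promise are partly answerable, not unanswerable. That conclusion follows from the structure of the comparison and depends on no assumed figure, only on no reference arm being intended. If one is intended, the defect is an omission in the text.

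A reference arm would not make the study decisive at the lower N. Under the assumptions above, a 5-point effect at N=1000 would usually be missed (about 20% power, or 12% if N is shared equally between rounds), and the gain is an estimate with an interval. At N=3500 the corresponding figures are 56% and 31%. In a minimal-risk pilot survey this is a change that should be made, not a reason to stop.

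**What to change.** 1. **Section 11.** For the round that tests messages, add one randomised reference arm within the same N, or identify it if already intended. It should have the same imagined visit, the same availability statement and the same re-ask, but no recommendation or persuasive text. List the final messages once the first round has produced them. If no such arm is used, state that conclusions are limited to relative effectiveness.

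2. **Section 13.** Make each message versus the reference the main contrasts. Estimate them from one regression of post-message intent adjusted for pre-message intent (for a yes/no item, a linear risk-difference model with robust standard errors), with Holm or Dunnett. Keep between-message comparisons as secondary. Report the same contrasts among participants hesitant at the first ask, because Objective 2 concerns them, and accept that they will be less precise. If a participant sees more than one message, analyse the first or model repeated measures and order.

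**Cost.** One more survey branch and some analysis wording, with no extra participants. With four messages, each arm falls from 250 to 200 (N=1000) or from 875 to 700 (N=3500), with the loss of precision shown in the working. Baseline adjustment uses data already collected and is worth having whether or not the arm is added.

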- Adult (age 18 and over) who are members of an online panel (Prolific). Members of this panel joined the panel specifically to receive invitations to participate in research surveys and similar activities.
- Able to complete an online survey in English.

Exclusion Criteria.

- None

Children

This study will not include children. The study is restricted to adults aged 18 and over.

Prisoners

We will not knowingly conduct research on prisoners, however it is possible that prisoners are members of the existing internet research panel.

Pregnant Women

It is possible that data will be collected on pregnant women as they may have enrolled for the existing internet research panel which we will use.

Non-English speaking subjects

Participants will need to be able to complete an online survey in English. Due to the nature of the study (internally funded) we will not have the capacity to translate the survey into other languages.

7. Study-Wide Number of Subjects*

N/A; this is not a multi-site study.

8. Study-Wide Recruitment Methods*

N/A

9. Study Timelines*

Individuals who are members of an online research panel will be invited to complete an online survey. The survey will take approximately 20 minutes to complete. Because the topic (COVID-19 vaccine hesitancy) is rapidly changing, we may re-contact some participants to allow longitudinal data collection. Participants will be notified that they may be invited to respond to additional studies; participation in each survey will be voluntary. Invitations to a second survey will be distributed through the online panel platform, and will not require participants to provide any identifiable information to the research team. We anticipate completing this study in one year.

10. Study Endpoints*

Primary endpoint: Intent to be vaccinated against COVID-19.

Secondary endpoint: Predictors of intent to be vaccinated against COVID-19, including knowledge, attitudes, and beliefs about COVID-19, vaccines (in general), and a COVID-19 vaccine.

11. Procedures Involved*

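### Section 13 allows but does not commit to using pre-message intent in the randomised message comparison; unadjusted tests stay valid but may be less precise

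*Combined protocol and SAP*

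**What the plan says.** Section 10 sets "Primary endpoint: Intent to be vaccinated against COVID-19". Section 11 says the survey covers "intent to be vaccinated when a COVID-19 vaccine is available". It then says "Participants will be randomized to several brief, hypothetical messages", after which "intent to be vaccinated will be re-assessed". Table 1 in that section lists vaccination intent and message testing as separate domains. Section 13 will compare the messages "using t-tests, chi-squares, and regression models to compare vaccination intent according to which message participants received" and adds: "Appropriate statistical tests will be chosen depending on specific variables and their distributions". No section names pre-message intent as a covariate, says whether the outcome is post-message intent or change, or says which method is primary.

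On who is compared, Section 4 aims to "Develop and test messages that effectively address concerns of vaccine-hesitant subgroups at risk for declining to be vaccinated", while Section 13 does not restrict the comparison to hesitant respondents.

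**The concern.** Re-assessment implies an earlier assessment, so the design appears to collect, before randomisation takes effect, what is usually the strongest predictor of the outcome. Run on post-message answers, two of the three methods named in Section 13 cannot use it. A t-test on change scores does use it, but less efficiently than adjustment, and at low pre/post correlation it does worse than ignoring the earlier answer.

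At stake is the power to tell messages apart. Section 5 says of the second round that "we will test different versions of messages intended to reduce vaccine hesitancy and support uptake", and the tested messages are to be offered to organisations and providers. With as few as 1,000 respondents split over several messages, each pairwise comparison may be small.

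**Working it through.** **Inputs.** The plan has no figure of its own to reproduce: it gives no significance level, power, effect size, number of arms, response scale or pre/post correlation. From the documents: 57% intending to be vaccinated in the team's earlier survey (Section 5), and 1,000 to 3,500 respondents (Section 25). Assumed: four equal arms with one message each (250 or 875 per arm), three-level intent (15% no, 28% unsure, 57% yes), pairwise two-sided 5% tests, and a bivariate-normal model of pre- and post-message intent cut at 15% and 43%, with latent correlation ρ from 0.3 to 0.9.

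**Step 1: algebra for a continuous score.** With n per arm, the same SD σ before and after, and observed correlation r, the variance of an arm difference is:

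- unadjusted: 2σ²/n
- change score: (2σ²/n) × 2(1 − r)
- adjusted for pre-message intent: (2σ²/n) × (1 − r²)

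Since 2(1 − r) − (1 − r²) = (1 − r)² ≥ 0, adjustment is never less efficient than change. Change is worse than no adjustment when r < 0.5. The difference detectable with 80% power at 250 per arm is (1.960 + 0.842) × √(2/250) = 0.251 SD unadjusted. Adjusted, it is 0.251 × √(1 − 0.5²) = 0.217 SD at r = 0.5 and 0.251 × √(1 − 0.7²) = 0.179 SD at r = 0.7. At 875 per arm the three values are 0.134, 0.116 and 0.096 SD.

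**Step 2: a three-level item.** A coarse scale recovers less. If R² is the share of post-message variance explained by pre-message category, 1,000 adjusted respondents are worth 1,000/(1 − R²) unadjusted ones. For the intent score (R² shown rounded):

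| ρ | R², all | Worth | R², not already yes | Worth |
|---|---|---|---|---|
| 0.3 | 0.051 | 1,054 | 0.017 | 1,017 |
| 0.5 | 0.152 | 1,180 | 0.055 | 1,058 |
| 0.7 | 0.329 | 1,489 | 0.133 | 1,153 |
| 0.8 | 0.456 | 1,837 | 0.202 | 1,253 |
| 0.9 | 0.621 | 2,637 | 0.317 | 1,465 |

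For a yes/no outcome the ranges are 1,045 to 2,122 (all) and 1,013 to 1,103 (not already yes). Splitting the other 43% as 10/33, 21.5/21.5 or 28/15 gives about 1,048 to 2,710 and 1,011 to 1,433 on the score.

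**Step 3: power by simulation** (10,000 runs per setting, standard error at most 0.5 points). A 0.2 SD latent shift raises yes from 57% by 7.7 points. All respondents, 250 per arm:

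| Method | ρ = 0.3 | 0.5 | 0.7 | 0.8 | 0.9 |
|---|---|---|---|---|---|
| Adjusted linear | 48% | 52% | 63% | 71% | 85% |
| Adjusted logistic, standardised difference | 44% | 47% | 55% | 60% | 73% |
| Change score | 31% | 37% | 51% | 61% | 79% |

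The unadjusted t-test has 46–47% and the chi-square 41–42% throughout.

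- All respondents, 875 per arm: at 0.1 SD, 37–43% unadjusted against 39–82% adjusted; at 0.2 SD, 90–94% against 92–100%.
- Only those not already yes, 0.43 × 250 ≈ 108 per arm, 0.2 SD: t-test 27, 30, 37, 43, 53% against adjusted linear 27, 31, 41, 52, 70% as ρ rises.

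**Step 4: validity.** With no message effect, every method rejected in 4.7–5.7% of runs.

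**Step 5: the quantity reported.** In the 0.2 SD setting with 250 per arm, the marginal odds ratio is 1.38, but adjusted logistic regression gives a conditional odds ratio of 1.41, 1.45, 1.57, 1.69 and 2.02 as ρ rises. The standardised difference in yes averages 7.6–7.7 points against a true 7.7. A bare adjusted odds ratio would therefore change the quantity reported; the standardised difference does not.

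**The case against.** The strongest reply is that nothing here is an error. Regression is on the list, no passage plans to ignore the earlier answer, the title calls this a pilot, and the loss depends on a choice not yet made. That is true, and it is why the point concerns efficiency only. But permission is not a plan, and the named alternatives can do worse at no saving.

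Second, the size rests on assumptions and may be negligible. This stands. Among respondents not already answering yes, where the second objective points, a yes/no outcome gains at most about 10% (1,103 per 1,000). With 875 per arm and a 0.2 SD effect, unadjusted power is already at least 90%. The large gains need stable answers and a comparison of all respondents, which the plan does not exclude.

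Third, the pre-message measure is inferred. Item order and post-message wording are not given, and Table 1 shows sample items only. Its intent item asks about a vaccine once one becomes available, while its sample message offers one that day. If the two questions differ, the correlation may be lower. Section 10 also does not say that the primary endpoint is the post-message answer. These points weaken confidence in the size, not in the recommendation.

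Fourth, the handling of skipped answers can be debated. With 10% of pre-message answers skipped at random (250 per arm, 0.2 SD), giving them their own category had 49, 52, 60 and 80% power at ρ = 0.3, 0.5, 0.7 and 0.9, against 45, 48, 57 and 82% when skippers were dropped. Dropping wins slightly at 0.9, but it discards randomised respondents. When skipping was concentrated among those answering no, its estimates were 0.115–0.117 against a true 0.1185, compared with 0.117–0.118 for the own-category coding.

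**Conclusion.** The concern holds. Section 13 permits adjustment for pre-message intent without committing to it. The consequence is a possible loss of precision in the message comparison, not bias or an inflated type I error. The loss runs from trivial to large: small if pre- and post-message answers correlate weakly, if only hesitant respondents are compared, or near 3,500 respondents with a larger effect; large if answers are stable, everyone is compared, and the sample is near 1,000 or the effect is small. In the main comparisons simulated, the adjusted linear model did not lose to the t-test.

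Confidence is medium. The arm count, scale, split and correlation are assumed, and the pre-message item is inferred from the re-assessment wording. Validity of the unadjusted tests assumes one message per person, as Section 13 suggests; if each person rated several messages, independent-sample tests would have to allow for within-person correlation.

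**What to change.** In Section 13:

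- Make the primary message comparison a regression of post-message intent on message arm, with pre-message intent as a categorical covariate and a skipped answer as its own category.
- If intent is analysed as a score, use a linear model and report the adjusted mean difference. If it is yes/no or ordinal, use a logistic or ordinal model and report the standardised (marginal) difference in the proportion answering yes.
- State whether all respondents or only those not already answering yes are compared.
- Keep unadjusted t-tests and chi-squares as secondary, and do not make change scores primary.

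The cost is two or three sentences of analysis wording, with no extra data or respondents. It also removes the freedom to choose between adjusted, unadjusted and change analyses after seeing the results.
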